### 8.1.3. Unexpected Adverse Events

Unexpected AEs are those events that are not consistent with the Reference Safety Information (RSI) for the medicinal product, or the nature, severity, or outcome of which is not consistent with the expected events as per the RSI. For ataluren, the RSI is the Table of Adverse Reactions in Section 4.8 of the SmPC

A copy of the SmPC (version dated 17 June 2021) is included in the current protocol in Appendix A.

## 8.2. Eliciting Adverse Event Information

The investigator is to report all directly observed AEs and all AEs spontaneously reported by the study subject or parent/guardian in case of a child. In addition, each study subject will be questioned about AEs at each scheduled clinic visit after ataluren administration or during each

telephone contact with the subject or parent/guardian in case of a child. The type of question asked should be open-ended, e.g., “*How has your child been feeling?*” or a similar type of query.

### **8.3. Adverse Event Recording**

All AEs (both serious and non-serious) that occur in subjects during the AE reporting period must be recorded, whether or not the event is considered drug related. All AEs are to be recorded in the source documents and the CRF using concise medical terminology; whenever possible terms contained in Medical Dictionary for Regulatory Activities (MedDRA) should be employed.

In addition, the following information should be recorded:

- Indication of whether the event is serious or non-serious (see Section 8.1)
- Relationship to ataluren (see Section 8.4)
- Severity of the event (see Section 8.5)
- Onset date
- Resolution date, or date of death
- Action taken
- Outcome of the event

Classification of the event as serious or non-serious determines the reporting procedures to be followed.

### **8.4. Describing Adverse Event Relationship to Study Drug**

Based on the considerations outlined in Table 4 below, the investigator should provide an assessment of the relationship of the AE to the study drug, i.e., whether there is a reasonable possibility that the study drug caused the AE.

**Table 4: Relationship of Study Drug to Adverse Event**

Relationship	Description
Probable	A clinical event in which a relationship to the study drug seems probable because of such factors as consistency with known effects of the drug; a clear temporal association with the use of the drug; improvement upon withdrawal of the drug; recurrence upon re-challenge with the drug; lack of alternative explanations for the event.
Possible	A clinical event occurring coincident with administration of the study drug and which may or may not be explained by concurrent disease or other drugs or chemicals. Information on drug withdrawal or re-challenge may be lacking.
Unlikely	A clinical event with a temporal relationship to the study drug exposure that does not preclude causality but for which there is a clear alternate cause that is more likely to have caused the adverse event than study drug. Such alternatives include a concomitantly administered drug, the subject's disease state, other medical conditions, or environmental factors.
Unrelated	A clinical event, for which a relationship to the study drug seems improbable because of factors such as inconsistency with known effects of the study drug, lack of a temporal association with study drug administration, lack of association of the event with study drug withdrawal or re-challenge, and/or presence of alternative explanations for the event. Alternative explanations might include a known relationship of the adverse event to a concomitant drug, past medical history of a similar event, the subject's disease state, other medical conditions, or environmental factors.

### 8.5. Grading of Severity of Adverse Events

The severity of AEs will be graded using the CTCAE, Version 5.0 ([https://ctep.cancer.gov/protocoldevelopment/electronic\\_applications/docs/CTCAE\\_v5\\_Quick\\_Reference\\_8.5x11.pdf](https://ctep.cancer.gov/protocoldevelopment/electronic_applications/docs/CTCAE_v5_Quick_Reference_8.5x11.pdf)). For each episode, the highest severity grade attained should be reported.

If a CTCAE criterion does not exist, the investigator should use the grade or adjectives: Grade 1 (mild), Grade 2 (moderate), Grade 3 (severe), Grade 4 (life-threatening), or Grade 5 (fatal) to describe the maximum intensity of the AE. For purposes of consistency with the CTCAE, these intensity grades are defined in Table 5.

**Table 5: Grading of Adverse Event Severity**

Grade	Adjective	Description
Grade 1	Mild	Sign or symptom is present, but it is easily tolerated, is not expected to have a clinically significant effect on the subject's overall health and well-being, does not interfere with the subject's usual function, and is not likely to require medical attention
Grade 2	Moderate	Sign or symptom causes interference with usual activity or affect clinical status, and may require medical intervention
Grade 3	Severe	Sign or symptom is incapacitating or significantly affects clinical status and likely requires medical intervention and/or close follow-up
Grade 4	Life-threatening	Sign or symptom results in a potential threat to life
Grade 5	Fatal	Sign or symptom results in death

Note the distinction between the seriousness and the severity of an AE. Severe is a measure of intensity; thus, a severe reaction is not necessarily a serious reaction. For example, a headache may be severe in intensity, but would not be classified as serious unless it met one of the criteria for serious events listed in Section 8.1 above.

### 8.6. Follow-up of Unresolved Adverse Events

All AE should be followed up by the investigator until they are resolved, or the investigator assesses them as chronic or stable. Follow-up of any SAE that is fatal or life-threatening should be provided within one additional calendar week. The investigator should consider protocol guidelines and use his/her discretion in ordering additional tests as necessary to monitor the resolution of such events. In the event of additional investigations, the PTC medical monitor should be informed via e-mail. A subject withdrawn from the study because of an AE must be followed by the investigator until clinical recovery is complete and laboratory results have returned to normal, or until progression has been stabilized. Follow-up may need to continue after the subject has discontinued from the study, and additional investigations may be requested by the medical monitoring team.

### 8.7. Adverse Event Reporting Period

The first day of AE reporting will coincide with the day the informed consent is signed. The AE reporting period for this study ends 6 weeks after the last administration of the ataluren.

### 8.8. Site Adverse Event Reporting Requirements

Classification of an event as serious or non-serious (see Section 8.1) determines the reporting procedures to be followed. Site reporting requirements for AEs are summarized in Table 6 below.

**Table 6: Site Reporting Requirements for Adverse Events**

Event	Recorded on the eCRF	Reported on the SAE/Pregnancy Report Form to PTC Pharmacovigilance Within 24 Hours of Awareness
Serious AE	All	All
Non-Serious AE	All	None
Other, eg, paternal exposure before/during pregnancy, or occupational exposure	All (regardless of whether associated with an AE), except occupational exposure	All (regardless of whether associated with an AE)

**Abbreviations:** AE, adverse event; eCRF, electronic case report form; SAE, serious adverse event

### 8.9. Serious Adverse Event Reporting

All SAEs should be reported via the SAE form to PTC Therapeutics within 24 hours of becoming aware of the event(s).

In addition to completing the AE portion of the CRF, the SAE report form must also be completed. The SAE report form should be signed by the investigator; however, if the investigator is unable to sign at the time of the event or within 24 hours, the form should be signed by the clinical staff member reporting the SAE (e.g., the study coordinator). The SAE report form must be emailed or faxed to the PTC Therapeutics Pharmacovigilance Department and to the site IRB/IEC (if required by local regulations) within 24 hours. Follow up information to the SAE should be clearly documented as “follow up” in the SAE report form and must also be emailed or faxed to these same parties. All follow up SAE report forms for the event must be signed by the investigator. Any source documents (e.g., progress notes, nurses’ notes, laboratory and diagnostic test results, discharge summaries) should be redacted so that the subject’s name, address, and other personal identity information are obscured. Only the subject’s study number and initials are to be provided. The information in the AE portion of the CRF and the SAE report form(s) must match or be reconciled. Where the same data are collected, the forms must be completed in a consistent manner. For example, the same AE term should be used on both forms.

In the rare event that the investigator does not become aware of the occurrence of an SAE immediately (for example, if a subject initially seeks treatment elsewhere), the investigator is to report the event within 24 hours after learning of it and to document his/her first awareness of the AE.

The PTC Therapeutics contact information for reporting SAEs is listed below and is also provided in the Study Manual and in the SAE report form.

**PTC Therapeutics Safety Department**  
**Attention: Pharmacovigilance**  
**E-mail: [contact]**  
**[contact]**

#### **8.10. Reporting Pregnancy**

PTC Therapeutics should be notified in the event that a female partner of a subject becomes pregnant at any time after the subject’s first dose of study drug. Any such pregnancy occurring on study or within 30 days of the last administration of study drug must be reported on a Pregnancy Notification Form. This must be done whether or not an AE has occurred and within 24 hours of awareness of the pregnancy. The information submitted should include the anticipated date of birth or pregnancy termination.

Written consent is required prior to collecting and reporting any information on a female partner of a subject.

If possible, the investigator should follow the pregnant female partner of the subject until completion of the pregnancy and notify the PTC Therapeutics medical monitor of the outcome within 5 days or as specified below. The investigator will provide this information as a follow--up to the initial Pregnancy Notification Form via the Pregnancy Outcome Form (see Study Manual for details).

If the outcome of the pregnancy meets the criteria for immediate classification as an SAE (i.e., spontaneous abortion, stillbirth, neonatal death, or congenital anomaly [including that in an aborted fetus]), the investigator should follow the procedures for reporting SAEs, i.e., report the event to the PTC Therapeutics Safety Department or designee and follow up by submission of appropriate AE CRFs.

### **8.11. PTC Therapeutics Adverse Event Reporting Requirements**

As the sponsor of the study, PTC Therapeutics is responsible for reporting certain safety information, particularly SAEs and subject deaths related to participation in the study, to each investigator in an expedited manner. If notification of an AE requiring expedited reporting to investigators is received, PTC Therapeutics will contact each investigator site participating in this study by e-mail, fax, and/or overnight mail such that the investigator can promptly notify the site IRB/IEC per their local requirements. The initial expedited safety report will be provided as required according to local regulations (e.g., within 15 days) after the earliest date PTC Therapeutics or an agent of PTC Therapeutics (e.g., a site monitor) becomes aware of an AE. This awareness date is the date the regulatory reporting clock begins and the date is considered Day 0.

## 9. WITHDRAWAL OF SUBJECTS

All subjects who receive ataluren should remain in the study whenever possible. However:

- The subject has the right to withdraw consent and discontinue ataluren at any time.
- If the subject's condition substantially worsens after initiating ataluren treatment, the subject will be carefully evaluated by the investigator. The subject will be withdrawn from treatment if continuing would place them at risk.
- The investigator may withdraw the subject from ataluren treatment, if, in the investigator's clinical judgment, it is not in the subject's best interest to continue or if the subject is not complying with the protocol (ie, per protocol visits, return of unused study drug).
- If the subject is unable to tolerate ataluren, he will be withdrawn from treatment.
- The subject is eligible to participate in another ataluren - nmDBMD clinical trial program initiated by PTC Therapeutics.
- The relevant regulatory authority and/or PTC Therapeutics may discontinue the study at any time.
- The study will be stopped once ataluren becomes commercially available.

The date the subject is withdrawn from the study and the reason for discontinuation will be recorded in the source documents and in the CRFs. The PTC medical monitor should be informed via e-mail of when a subject is withdrawn from the study.

When ataluren is discontinued (regardless of the reason), the investigator is expected to capture all of the evaluations required at the Discontinuation Visit and that any additional evaluations be completed that may be necessary to ensure that the subject is free of untoward effects. The subject should be encouraged to seek appropriate follow-up for any continuing health problems.

## **10. STATISTICS AND DATA MANAGEMENT**

### **10.1. Sample Size Calculation for the Primary Endpoint**

The sample size for this study is based on the number of subjects in previous ataluren DBMD studies and is not based upon any formal statistical hypothesis.

### **10.2. Study Population Definition**

#### **10.2.1. As-Treated Population**

The as-treated population consists of all subjects who receive at least 1 dose of ataluren. This population will be evaluated in the analyses of safety (the primary endpoint) and treatment administration.

### **10.3. General Statistical Considerations**

By-subject listings will be created for each CRF module.

Summary tables for continuous variables, overall and by corticosteroid use, will contain the following statistics: n, mean, standard deviation, standard error, 95% confidence intervals on the mean, median, minimum, and maximum. In addition, changes from baseline will be likewise summarized. If continuous data have substantial non-normality, log-transformed data or nonparametric tests may be employed, as appropriate.

Summary tables for categorical variables, overall and by corticosteroid use, will include N, n, and percentages.

Unless otherwise specified, all analyses will be 2-sided at the 0.05 level of significance.

### **10.4. Specific Statistical Analyses**

#### **10.4.1. Study Conduct and Subject Disposition**

Subjects who discontinue ataluren or are removed from the study prematurely will also be reported. Reasons for screening failures and early discontinuations, and time of withdrawal from study will be described.

#### **10.4.2. Baseline Characteristics**

Subject characteristics at entry into the study will be summarized in frequency tables and descriptive statistics will be provided for quantitative variables.

#### **10.4.3. Study Treatment Administration**

For each subject, ataluren administration will be described in terms of the total duration of therapy, dose modifications, dose delays, and dose omissions; and reasons for deviations from planned therapy.

#### **10.4.4. Use of Concomitant Medication and Supportive Therapy**

Concomitant medications will be coded using the World Health Organization Drug Dictionary (WHODRUG) dictionary into Anatomical-Therapeutic-Chemical classification (ATC) codes. The type and timing of use of specific concomitant medications will be listed and summarized.

Specific attention will be focused on corticosteroid use and use of drugs for prophylaxis/treatment of CHF. The type and duration of pre-study use will be described. The type, dose, schedule, duration of use, dose modifications, dose omissions, and reasons for deviations from initial therapy will be described.

#### **10.4.5. Primary Variables**

##### ***10.4.5.1. Adverse Events***

Adverse events will be classified using the MedDRA classification system. The severity of AEs will be graded according to the CTCAE, Version 5.0 whenever possible. A treatment-emergent adverse event is defined as an AE that occurs or worsens in the period extending from a subject's first ataluren dose in this study to 6 weeks after the last ataluren dose in this study.

The frequency of subjects experiencing a specific AE will be tabulated by visit, body system, and MedDRA term. In the by-subject analysis, a subject having the same event more than once will be counted only once using the worst CTCAE grade.

Adverse events classified as CTCAE Grade 3 or higher; study-drug-related events; adrenal, hepatic, and renal events leading to special diagnostic evaluations; events leading to discontinuation from treatment; and SAEs will be considered with special attention.

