### **3. STUDY DESIGN**

This study comprises an open-label, safety study of ataluren in subjects who previously received ataluren at an investigational site in a prior PTC-sponsored clinical study or treatment plan and siblings of those subjects. Only subjects enrolling in the current study from [PTC124-GD-048-DMD](#) (Study 048) will have efficacy assessments (ie, [Peabody Developmental Motor Scale](#), second edition [PDMS-2]) performed for up to 52 weeks from the date of first dosing in Study 048.

This study will be performed at investigational sites in the US and Canada. It is planned that approximately 270 subjects will be enrolled. Subjects will receive ataluren 3 times per day (TID) at respective morning, midday, and evening doses of 10 mg/kg, 10 mg/kg, and 20 mg/kg. Study assessments will be performed during screening, on the first day of ataluren dosing, and then every 12, 24, and 48 weeks as described in [Table 2](#).

For subjects from Study 048 only, study assessments will be performed and motor development will be assessed using the PDMS-2 at baseline/Day 1, Week 14, and Week 28. After the Week 28 visit, study assessments will be performed every 12, 24, and 48 weeks as described in [Table 3](#).

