### 4.2. Inclusion Criteria

Subjects must meet all of the following conditions to be eligible for enrollment into the study:

1. Evidence of signed and dated informed consent/assent document(s) indicating that the subject (and/or his parent/legal guardian) has been informed of all pertinent aspects of the trial. ***Note: If the study candidate is considered a child under local regulation, a parent or legal guardian must provide written consent prior to initiation of study screening procedures and the study candidate may be required to provide written assent. The rules of the responsible Institutional Review Board/Independent Ethic Committee (IRB/IEC) regarding whether one or both parents must provide consent and the appropriate ages for obtaining consent and assent from the subject should be followed.***
2. Subjects with nmDBMD and a history of exposure to ataluren in a prior PTC study or treatment plan and affected nmDBMD siblings of those subjects (provided those subjects have completed the placebo-controlled portion of the trial).
3. Male sex.
4. Fertile men, as defined in (CTFG 2020), who are sexually active with women of childbearing potential and who have not had a vasectomy, must agree to use a barrier method of birth control during the study and for up to 50 days after the last dose of study drug.
5. Willingness and ability to comply with scheduled visits, drug administration and return plan, study procedures, laboratory tests, and study restrictions. ***Note: Psychological, social, familial, or geographical factors that might preclude adequate study participation should be considered.***

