**Table 2: Schedule of Events**

Study Period	Screening	Baseline	Treatment				6 Weeks Post D/C
Study Week (±7 Days)	Day 1 a	Day 1 a	Every 12 Weeks	Every 24 Weeks	Every 48 Weeks b	End of TX	
Informed consent c	X	X					
Clinical history d	X	X					
Vital signs	X				X	X	X
Height	X						
Weight	X	X		X e	X	X	X
Physical examination	X						
Hepatitis B and C f	X						
Hematology	X				X	X	X
Biochemistry	X				X	X	X
Drug dispensed		X	X g	X g	X g		
Pre-/post-shipment communication			X h	X h	X h		
Drug compliance			X i	X i	X i	X	
Adverse events	X	X	X i	X i	X i	X	X
Concomitant medication	X	X	X i	X i	X i	X	X

**Abbreviations:** D/C, discontinuation; TX, treatment

a Subjects who have not participated in an ataluren study in the past year are required to complete all assessments identified under screening. Subjects who have participated in an ataluren study within the past year only need to complete the assessments identified under baseline.

b Annual visits will occur every 48 weeks (ie, Weeks 48, 96, 144, 192, 240, 288, 336, 384, 432, 480, 528, 576, 624, 672, 720, etc).

c Informed consent will be signed before any study procedures are performed.

d Clinical history will be collected for ataluren-naïve subjects (siblings). For subjects enrolling from another ataluren clinical study, only clinical history reported since the last dose of ataluren in the prior DBMD study will be collected.

e Reminders will be communicated prior to every 24 week visit for subject to obtain a weight check-in between the annual visits at sites. This communication will be documented in the source.

f Hepatitis B and C testing is only required for ataluren-naïve subjects (siblings) or subjects who have a temporary treatment gap of 1 year before entering Study 016.

g Drug will be dispensed to the subject every 12 weeks.

h Clinical site staff will contact the subject or parent(s)/legal guardian(s) to confirm details and timing of the upcoming study drug shipment. Post-shipment contact will confirm receipt of and condition of study drug.

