A preexisting condition (e.g., allergic rhinitis) must be noted on the appropriate CRF for Visit 1 but should not be reported as an AE unless the condition worsens or episodes increase in frequency during the AE reporting period. Diagnostic and therapeutic non-invasive and invasive procedures, such as surgery, should not be reported as AEs. However, the medical condition for which the procedure was performed should be reported if it meets the definition of an AE. For example, an acute appendicitis occurs during the treatment with study drug should be reported as the AE and the resulting appendectomy should be recorded in the source documents and CRF. If a surgical procedure was planned prior to entry into the study, and the surgery is not performed because of a worsening of a baseline condition, this should not be reported as an AE. Note that, as described in Section 8.1.2, any inpatient hospitalization occurring as the consequence of an AE during the study period should be reported as an SAE.

Each AE is to be classified as serious or non-serious by the investigator using medical and scientific judgment.

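### Safety tables pool ataluren-naive siblings with previously exposed subjects and restart treatment emergence at entry, so the risk of starting ataluren cannot be told apart from the risk of continuing it

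*Protocol*

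**What the plan says.** Section 3 describes the study population as "subjects who previously received ataluren at an investigational site in a prior PTC-sponsored clinical study or treatment plan and siblings of those subjects". Inclusion criterion 2 in section 4.2 is worded as "Subjects with nmDBMD and a history of exposure to ataluren in a prior PTC study or treatment plan and affected nmDBMD siblings of those subjects", on condition that the placebo-controlled part of the trial has been completed. Exclusion criterion 3 and the footnotes to Table 2 treat siblings as ataluren-naive and single out subjects with a one-year treatment gap.

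The analysis sections do not carry these distinctions forward. Section 10.2.1 says "The as-treated population consists of all subjects who receive at least 1 dose of ataluren", and this single population serves the primary endpoint, safety. Section 10.3 says "Summary tables for categorical variables, overall and by corticosteroid use, will include N, n, and percentages", with the same split for continuous variables.

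For adverse events, section 10.4.5.1 opens its definition with the words "A treatment-emergent adverse event is defined as an AE that occurs or worsens in the period extending from". Both ends of the period are then tied to the present trial and not to first exposure: it runs from the "first ataluren dose in this study to 6 weeks after the last ataluren dose in this study". Section 8.1.1 requires a pre-existing condition to be noted on the Visit 1 form, but it "should not be reported as an AE unless the condition worsens or episodes increase in frequency during the AE reporting period". Table 2, footnote d, limits the history taken from subjects of an earlier ataluren study to the time after their last dose there.

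**The concern.** The objective in section 2 names two kinds of subject: those with prior ataluren exposure and siblings. They put different questions to a safety study. A naive sibling shows what happens when ataluren is started. A previously exposed subject shows what happens when it is continued or resumed.

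The emergence rule also treats the same effect differently in the two groups. If it first appears in a sibling on drug, it enters the numerator. If it appeared in a roll-over subject during the parent study and is still there unchanged, it does not, yet that subject remains in the denominator. A reader of the pooled incidence table could take the result as the tolerability of ataluren in general, when its value depends partly on the enrolment mix.

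**Working it through.** There is no figure of the plan's own to reproduce. Section 10.1 states that the sample size is not based on a formal hypothesis, and the protocol gives no event rates and no sibling count. The check is therefore a reading of the rules followed by an illustration.

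**Step 1: what the rules count.** Sections 8.1.1 and 10.4.5.1 taken together:

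| Situation | Adverse event? | Treatment-emergent? |
|---|---|---|
| Began in parent study, unchanged since | No | No |
| Began in parent study, worse or more frequent after first dose here | Yes | Yes |
| Resolved before entry, returns after first dose here | Yes | Yes |
| First appears after first dose here, any subject | Yes | Yes |

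Only the first row falls out, and only a previously exposed subject can be in it with a drug effect. For scale, take all 270 as previously exposed and assume that 10% enter with such an effect: 0.10 × 270 = 27 subjects. If an assumed 10% to 30% of them worsen, 2.7 to 8.1 are counted as treatment-emergent and about 19 to 24 are not.

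**Step 2: what pooling does.** Let k be the number of naive siblings among the planned 270, p_n the risk in naive subjects and p_e the risk in previously exposed subjects. Then

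pooled = [k × p_n + (270 − k) × p_e] / 270 = p_e + (k/270) × (p_n − p_e).

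The pooled rate thus contains the fraction k/270 of any excess in naive subjects. Example with k = 20, p_n = 10%, p_e = 2%: (2 + 5)/270 = 2.6%. Apart from 270, every input in this table is an assumption:

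| k | k/270 | 10% v 2% | 20% v 5% | 5% v 5% |
|---|---|---|---|---|
| 5 | 1.9% | 2.1% | 5.3% | 5.0% |
| 10 | 3.7% | 2.3% | 5.6% | 5.0% |
| 20 | 7.4% | 2.6% | 6.1% | 5.0% |
| 40 | 14.8% | 3.2% | 7.2% | 5.0% |

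The last column is the null case: equal risks, no dilution. The pooled table alone cannot tell a reader which column applies.

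**Step 3: what separate reporting costs.** With no events among n subjects, the one-sided 95% upper bound is 1 − 0.05^(1/n). For n = 5, 10, 20 and 40 this is 45%, 26%, 14% and 7.2%, against 1.1% for n = 270. The sibling results would be imprecise, but the table would show it.

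**The case against.** The strongest reply is that subgroup displays commonly belong in the analysis plan, which is not at hand. Naming corticosteroid use in section 10.3 does not forbid other splits. Nor does the objective claim to estimate first-exposure risk; it asks about safety in the subjects enrolled. This stands in part: the absence of a prior-exposure split is not an error in itself. But the emergence definition is fixed in the protocol, and an analysis plan would inherit it. The protocol already separates these groups for screening, history and hepatitis testing, then names a different factor for its tables.

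Several stronger readings are tempting and are not supported:

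- *Everything that began in a parent study is lost.* No. Effects that worsen, become more frequent or return are counted. Unchanged ones belong on the Visit 1 form, and section 10.3 provides listings for every form module. They are missing from the incidence tables, not from the record.
- *A carried-over laboratory grade becomes the baseline grade and hides the shift.* Table 2 marks no hematology or biochemistry in the baseline column, the only one required of subjects in an ataluren study within the past year, and Table 3 marks none at Day 1. Section 10.4.5.2 does not say which value is used instead. Its worst-grade tables do not depend on baseline at all.
- *Roll-over subjects are survivors who tolerated the drug.* Plausible, but section 4.2 requires exposure, not tolerance or completion of treatment.
- *Pooling biases the result towards safety by a known amount.* It does so only if first-exposure risk is higher, and no rate or sibling count is given.
- *Subjects never dosed here enter the as-treated population.* Section 10.2.1 omits the words that tie the dose to this study, but its purpose is plain. This is a drafting matter.

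**Conclusion.** The point holds in a limited form. As written, the treatment-emergent tables cannot include a stable ataluren effect carried over from a parent study, and the pooled incidence cannot separate starting ataluren from continuing it. Both follow from the protocol's own text.

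The size cannot be determined. For an assumed 5 to 40 siblings, the pooled rate carries 1.9% to 14.8% of any excess risk in naive subjects, and the distortion is zero if the risks are equal. The number of stable carry-over effects is likewise unknown. Neither the safety data nor the study objective is invalidated. Separate reporting is nonetheless a concrete and inexpensive improvement in a study whose primary endpoint is safety and whose objective names both groups.

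**What to change.** In sections 10.3 and 10.4.5, add summaries of adverse events, laboratory data and exposure by prior-exposure group, beside the pooled results:

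- ataluren-naive siblings;
- subjects returning after a gap of 1 year or more;
- subjects continuing, or with a gap under 1 year.

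For previously exposed subjects, list the adverse events ongoing at Day 1 with their parent-study onset date and relatedness. State in section 10.4.5.1 that treatment-emergent rates in these subjects describe continued or resumed treatment, not first exposure.

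Two further changes are optional or editorial. An integrated analysis counted from the first-ever ataluren dose would be informative but is not needed to cure the point. Adding that the dose is one given in this study would clarify section 10.2.1.

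The cost is wording, programming and linkage to parent-study records; section 5.2 gives each subject a number for this study, so a cross-reference to the earlier number is needed. No visit, assessment or clinical rule changes. The statistical price is small sibling cells with the wide intervals shown above, which should be presented descriptively.
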